### 7.2.3 Immediate Reporting of Adverse Events to the Sponsor, Vasgene Therapeutics and to Merck

#### 7.2.3.1 Serious Adverse Events

A serious adverse event is any adverse event occurring at any dose or during any use of Vasgene's and/or Merck's product that:

- Results in death;
- Is life threatening;
- Results in persistent or significant disability/incapacity;
- Results in or prolongs an existing inpatient hospitalization;
- Is a congenital anomaly/birth defect;
- Is an other important medical event
- **Note:** In addition to the above criteria, adverse events meeting either of the below criteria, although not serious per ICH definition, are reportable to the Merck in the same timeframe as SAEs to meet certain local requirements. Therefore, these events are considered serious by Merck for collection purposes.
  - Is a new cancer (that is not a condition of the study);
  - Is associated with an overdose.

Refer to Table 6 for additional details regarding each of the above criteria.

For the time period beginning when the consent form is signed until treatment allocation/randomization, any serious adverse event, or follow up to a serious adverse event, including death due to any cause other than progression of the cancer under study, that occurs to any subject must be reported within 24 hours to the Sponsor, Vasgene Therapeutics and within 2 working days to Merck Global Safety if it causes the subject to be excluded from the trial, or is the result of a protocol-specified intervention, including but not limited to washout or discontinuation of usual therapy, diet, placebo treatment or a procedure.

For the time period beginning at treatment allocation/randomization through 90 days following cessation of treatment, or 30 days following cessation of treatment if the subject initiates new anticancer therapy, whichever is earlier, any serious adverse event, or follow up to a serious adverse event, including death due to any cause other than progression of the cancer under, whether or not related to the Vasgene Therapeutics product and/or Merck product, must be reported within 24 hours to the Sponsor, Vasgene Therapeutics and within 2 working days to Merck Global Safety.

Additionally, any serious adverse event, considered by an investigator who is a qualified physician to be related to Merck and/or Vasgene product that is brought to the attention of the investigator at any time following consent through the end of the specified safety follow-up period specified in the paragraph above, or at any time outside of the time period specified in the previous paragraph also must be reported immediately to the Sponsor, Vasgene Therapeutics and to Merck Global Safety.

All subjects with serious adverse events must be followed up for outcome.

**SAE Notification to Merck and Vasgene Therapeutics Inc:**

All investigate sites are required to complete MedWatch 3500A (Mandatory Reporting Form) for SAEs. All sites must submit the form as two separate communications: 1) Vasgene Therapeutics, Inc. within 24hr of site becoming aware of the event 2) Merck Global Safety within 2 working days of becoming aware of the event. Please see the Appendix for SAE cover forms.

**SAE notification to the FDA:**

- USC: Study team to work with CISO QA to submit to the FDA using MedWatch 3500A form in accordance within the FDA required timelines

**SAE reports and any other relevant safety information are to be forwarded to the Merck**

A copy of all 15 Day Reports and Annual Progress Reports is submitted as required by FDA, European Union (EU), Pharmaceutical and Medical Devices agency (PMDA) or other local regulators. Investigators will cross reference this submission according to local regulations to the Merck Investigational Compound Number (IND, CSA, etc.) at the time of submission. Additionally investigators will submit a copy of these reports to Merck & Co., Inc. (Attn: Worldwide Product Safety; [contact]) at the time of submission to FDA.

### **7.2.3.2 Events of Clinical Interest**

Selected non-serious and serious adverse events are also known as Events of Clinical Interest (ECI) and must be reported within 24 hours to the Sponsor, Vasgene Therapeutics and within 2 working days to Merck Global Safety. (Attn: Worldwide Product Safety; [contact]).

For the time period beginning when the consent form is signed until treatment allocation/randomization, any ECI, or follow up to an ECI, that occurs to any subject must be reported within 24 hours to the Sponsor, Vasgene Therapeutics and within 2 working days to Merck Global Safety if it causes the subject to be excluded from the trial, or is the result of a protocol-specified intervention, including but not limited to washout or discontinuation of usual therapy, diet, placebo treatment or a procedure.

For the time period beginning at treatment allocation/randomization through 90 days following cessation of treatment, or 30 days following cessation of treatment if the subject initiates new anticancer therapy, whichever is earlier, any ECI, or follow up to an ECI, whether or not related to Merck and Vasgene product, must be reported within 24 hours to the Sponsor, Vasgene Therapeutics and within 24 hours to Merck Global Safety.

Events of clinical interest for this trial include:

1. an overdose of Merck product, as defined in Section 7.2.1 - Definition of an Overdose for This Protocol and Reporting of Overdose to the Sponsor, that is not associated with clinical symptoms or abnormal laboratory results.
2. an elevated AST or ALT lab value that is greater than or equal to 3X the upper limit of normal and an elevated total bilirubin lab value that is greater than or equal to 2X the upper limit of normal and, at the same time, an alkaline phosphatase lab value that is less than 2X the upper limit of normal, as determined by way of protocol-specified laboratory testing or unscheduled laboratory testing.\*

\*Note: These criteria are based upon available regulatory guidance documents. The purpose of the criteria is to specify a threshold of abnormal hepatic tests that may require an additional evaluation for an underlying etiology.

### **7.2.3.3 Protocol-Specific Exceptions to Serious Adverse Event Reporting**

Efficacy endpoints as outlined in this section will not be reported to Merck as described in Section 7.2.3.- Immediate Reporting of Adverse Events to the Sponsor and to Merck, unless there is evidence suggesting a causal relationship between the drug and the event. Any such event will be submitted to the Sponsor within 24 hours and to Merck Global Safety within 2 working days either by electronic or paper media.

Specifically, the suspected/actual events covered in this exception include any event that is disease progression of the cancer under study.

The Sponsor will monitor unblinded aggregated efficacy endpoint events and safety data to ensure the safety of the subjects in the trial. Any suspected endpoint which upon review is not progression of the cancer under study will be forwarded to Vasgene Therapeutics and Merck Global Safety as a SAE within 2 working days of determination that the event is not progression of the cancer under study

Hospitalization related to convenience (e.g. transportation issues etc.) will not be considered a SAE.

### **7.2.4 Evaluating Adverse Events**

An investigator who is a qualified physician will evaluate all adverse events according to the NCI Common Terminology for Adverse Events (CTCAE), version 4.0. Any adverse event which changes CTCAE grade over the course of a given episode will have each change of grade recorded on the adverse event case report forms/worksheets.

All adverse events regardless of CTCAE grade must also be evaluated for seriousness.

Table 6 Evaluating Adverse Events

An investigator who is a qualified physician, will evaluate all adverse events as to:

V4.0 CTCAE Grading	Grade 1	Mild; asymptomatic or mild symptoms; clinical or diagnostic observations only; intervention not indicated.
	Grade 2	Moderate; minimal, local or noninvasive intervention indicated; limiting age-appropriate instrumental ADL.
	Grade 3	Severe or medically significant but not immediately life-threatening; hospitalization or prolongation of hospitalization indicated; disabling; limiting self-care ADL.
	Grade 4	Life threatening consequences; urgent intervention indicated.
	Grade 5	Death related to AE
Seriousness	A serious adverse event is any adverse event occurring at any dose or during any use of Merck product that:	
	† Results in death; or	
	† Is life threatening; or places the subject, in the view of the investigator, at immediate risk of death from the event as it occurred (Note: This does not include an adverse event that, had it occurred in a more severe form, might have caused death.); or	
	† Results in a persistent or significant disability/incapacity (substantial disruption of one's ability to conduct normal life functions); or	
	† Results in or prolongs an existing inpatient hospitalization (hospitalization is defined as an inpatient admission, regardless of length of stay, even if the hospitalization is a precautionary measure for continued observation. (Note: Hospitalization for an elective procedure to treat a pre-existing condition that has not worsened is not a serious adverse event. A pre-existing condition is a clinical condition that is diagnosed prior to the use of a Merck product and is documented in the patient's medical history.); or	
	† Is a congenital anomaly/birth defect (in offspring of subject taking the product regardless of time to diagnosis); or	
	Is a new cancer (that is not a condition of the study) (although not serious per ICH definition, is reportable to the Sponsor within 24 hours and to Merck within 2 working days to meet certain local requirements); or	
	Is an overdose (whether accidental or intentional). Any adverse event associated with an overdose is considered a serious adverse event for collection purposes. An overdose that is not associated with an adverse event is considered a non-serious event of clinical interest and must be reported within 24 hours to the Sponsor and to Merck within 2 working days..	

	Other important medical events that may not result in death, not be life threatening, or not require hospitalization may be considered a serious adverse event when, based upon appropriate medical judgment, the event may jeopardize the subject and may require medical or surgical intervention to prevent one of the outcomes listed previously (designated above by a †).						
Duration	Record the start and stop dates of the adverse event. If less than 1 day, indicate the appropriate length of time and units						
Action taken	Did the adverse event cause Merck product to be discontinued?						
Relationship to Merck Product	
Did Merck product cause the adverse event? The determination of the likelihood that Merck product caused the adverse event will be provided by an investigator who is a qualified physician. The investigator's signed/dated initials on the source document or worksheet that supports the causality noted on the AE form, ensures that a medically qualified assessment of causality was done. This initialed document must be retained for the required regulatory time frame. The criteria below are intended as reference guidelines to assist the investigator in assessing the likelihood of a relationship between the test drug and the adverse event based upon the available information.
 
The following components are to be used to assess the relationship between Merck product and the AE; the greater the correlation with the components and their respective elements (in number and/or intensity), the more likely Merck product caused the adverse event (AE):
 
 
 Exposure	Is there evidence that the subject was actually exposed to Merck product such as: reliable history, acceptable compliance assessment (pill count, diary, etc.), expected pharmacologic effect, or measurement of drug/metabolite in bodily specimen?	
 
 Time Course	Did the AE follow in a reasonable temporal sequence from administration of Merck product? Is the time of onset of the AE compatible with a drug-induced effect (applies to trials with investigational medicinal product)?	
 
 Likely Cause	Is the AE not reasonably explained by another etiology such as underlying disease, other drug(s)/vaccine(s), or other host or environmental factors	
 
	Exposure	Is there evidence that the subject was actually exposed to Merck product such as: reliable history, acceptable compliance assessment (pill count, diary, etc.), expected pharmacologic effect, or measurement of drug/metabolite in bodily specimen?	Time Course	Did the AE follow in a reasonable temporal sequence from administration of Merck product? Is the time of onset of the AE compatible with a drug-induced effect (applies to trials with investigational medicinal product)?	Likely Cause	Is the AE not reasonably explained by another etiology such as underlying disease, other drug(s)/vaccine(s), or other host or environmental factors
Exposure	Is there evidence that the subject was actually exposed to Merck product such as: reliable history, acceptable compliance assessment (pill count, diary, etc.), expected pharmacologic effect, or measurement of drug/metabolite in bodily specimen?						
Time Course	Did the AE follow in a reasonable temporal sequence from administration of Merck product? Is the time of onset of the AE compatible with a drug-induced effect (applies to trials with investigational medicinal product)?						
Likely Cause	Is the AE not reasonably explained by another etiology such as underlying disease, other drug(s)/vaccine(s), or other host or environmental factors						

Relationship to Merck Product (continued)	The following components are to be used to assess the relationship between the test drug and the AE: (continued)	
	Dechallenge	
Was Merck product discontinued or dose/exposure/frequency reduced?
 
If yes, did the AE resolve or improve?
 
If yes, this is a positive dechallenge. If no, this is a negative dechallenge.
 
(Note: This criterion is not applicable if: (1) the AE resulted in death or permanent disability; (2) the AE resolved/improved despite continuation of the Sponsor's product; or (3) the trial is a single-dose drug trial); or (4) Sponsor's product(s) is/are only used one time.)

	Rechallenge	
Was the subject re-exposed to Merck product in this study?
 
If yes, did the AE recur or worsen?
 
If yes, this is a positive rechallenge. If no, this is a negative rechallenge.
 
(Note: This criterion is not applicable if: (1) the initial AE resulted in death or permanent disability, or (2) the trial is a single-dose drug trial); or (3) Sponsor's product(s) is/are used only one time).
 
NOTE: IF A RECHALLENGE IS PLANNED FOR AN ADVERSE EVENT WHICH WAS SERIOUS AND WHICH MAY HAVE BEEN CAUSED BY MERCK PRODUCT, OR IF REEXPOSURE TO MERCK PRODUCT POSES ADDITIONAL POTENTIAL SIGNIFICANT RISK TO THE SUBJECT, THEN THE RECHALLENGE MUST BE APPROVED IN ADVANCE BY THE SPONSOR AS PER DOSE MODIFICATION GUIDELINES IN THE PROTOCOL.

	Consistency with Trial Treatment Profile	Is the clinical/pathological presentation of the AE consistent with previous knowledge regarding Merck product or drug class pharmacology or toxicology?
The assessment of relationship will be reported on the case report forms /worksheets by an investigator who is a qualified physician according to his/her best clinical judgment, including consideration of the above elements.		
Record one of the following		Use the following scale of criteria as guidance (not all criteria must be present to be indicative of Merck product relationship).
Yes, there is a reasonable possibility of Merck product relationship.		There is evidence of exposure to Merck product. The temporal sequence of the AE onset relative to the administration of Merck product is reasonable. The AE is more likely explained by Merck product than by another cause.
No, there is not a reasonable possibility of Merck product relationship		Subject did not receive the Merck product OR temporal sequence of the AE onset relative to administration of Merck product is not reasonable OR the AE is more likely explained by another cause than the Merck product. (Also entered for a subject with overdose without an associated AE.)

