### 3.3 Safety Objective:

**Objective:** Determine the unique toxicities of the combination of pembrolizumab and sEphB4-HSA.

**Hypothesis:** The combination will have a low rate of adverse events that will be characterized by the sum of the anticipated toxicity of the two agents, without unique toxicity.

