## 7.2 Assessing and Recording Adverse Events

An adverse event is defined as any untoward medical occurrence in a patient or clinical investigation subject administered a pharmaceutical product and which does not necessarily have to have a causal relationship with this treatment. An adverse event can therefore be any unfavorable and unintended sign (including an abnormal laboratory finding, for example), symptom, or disease temporally associated with the use of a medicinal product or protocol-specified procedure, whether or not considered related to the medicinal product or protocol-specified procedure. Any worsening (i.e., any clinically significant adverse change in frequency and/or intensity) of a preexisting condition that is temporally associated with the use of the Vasgene's and/or Merck's product, is also an adverse event.

Changes resulting from normal growth and development that do not vary significantly in frequency or severity from expected levels are not to be considered adverse events. Examples of this may include, but are not limited to, teething, typical crying in infants and children and onset of menses or menopause occurring at a physiologically appropriate time.

Merck product includes any pharmaceutical product, biological product, device, diagnostic agent or protocol-specified procedure, whether investigational (including placebo or active comparator medication) or marketed, manufactured by, licensed by, provided by or distributed by Merck for human use.

Adverse events may occur during the course of the use of Merck product in clinical trials, or as prescribed in clinical practice, from overdose (whether accidental or intentional), from abuse and from withdrawal.

Progression of the cancer under study is not considered an adverse event.

All adverse events that occur after the consent form is signed but before treatment allocation/randomization must be reported by the investigator if they cause the subject to be excluded from the trial, or are the result of a protocol-specified intervention, including but not limited to washout or discontinuation of usual therapy, diet, placebo treatment or a procedure.

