### Toxicity Stopping Rules

Unacceptable toxicity is defined as drug related CTCAE v4.0 toxicity of grade 3 or more that does not resolve within 12 weeks. Patients who are removed from the trial for unacceptable toxicity and have not yet been evaluable for response will be classified as non-responders. We anticipate a drug related discontinuation rate of 10%.

For the purpose of assessing tolerability on an on-going manner and to have criteria to lead to review of all safety and toxicity in order to consider modifying the starting dose of either sEphB4-HSA or Pembrolizumab or both, unacceptable toxicity (TOX) will be defined as the inability to continue treatment to a 3rd course. Each cohort, a) lung and b) head/neck will be evaluated separately for:

- any toxicity (at least possibly related to treatment) that lead to treatment discontinuation prior to the start of the 3rd course
- inability for immune related toxicities to resolve within 42 days, during the 1st two courses.

Criteria for flagging an excessive number of patients with TOX are based on the sequential probability ratio test with  $\alpha=0.10$ ,  $\beta=0.10$ ,  $p_0=0.10$  and  $p_a=0.30$ . Every time a patient is classified as having had a TOX, the cumulative number of patients (X) who have experienced a TOX will be compared to the number of patients (N) who were enrolled at the time that the patient who experienced TOX, was enrolled. If the number of patients, N, is greater than  $N_X$ , the number given in the bottom row of the Table below, then the boundary has not been crossed. If N is less than or equal to  $N_X$ , then the boundary has been crossed and a careful review of all the toxicities and tolerability will be initiated.

Table: Boundary for Monitoring Safety/Tolerability				
X: # pts who experienced a TOX	3	4	5	6
N X : Boundary crossed if # pts. at risk (N) is $\leq N_X$	$\leq 7$	$\leq 12$	$\leq 18$	$\leq 23$

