## 9.0 LABELING, PACKAGING, STORAGE AND RETURN OF CLINICAL SUPPLIES

### 9.1 Investigational Product

The investigator shall take responsibility for and shall take all steps to maintain appropriate records and ensure appropriate supply, storage, handling, distribution and usage of investigational product in accordance with the protocol and any applicable laws and regulations.

Clinical Supplies will be provided by Merck and Vascene as summarized in Table 7.

Table 7 Product Descriptions

Product Name & Potency	Dosage Form
pembrolizumab 50 mg	Lyophilized Powder for Injection
pembrolizumab 100 mg/ 4mL	Solution for Injection
sEphB4-HSA 25 mg/mL	Solution in 10 mM L-Histidine, 150 mM Sodium Chloride, and 10% Sucrose, pH 7.0

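### Table 6 asks about causality and discontinuation for the Merck product only, so attribution to sEphB4-HSA and the action taken on it are not specified for adverse events generally

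*Combined protocol and SAP*

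**What the plan says.** Table 6 (Section 7.2.4) applies to all adverse events, and the relationship assessment it describes goes onto the case report forms or worksheets. On this point it contains:

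- **Causality:** "Did Merck product cause the adverse event". The answer is Yes or No. No applies, among other cases, when "the AE is more likely explained by another cause than the Merck product".
- **Alternative causes:** one component of the assessment asks "Is the AE not reasonably explained by another etiology such as underlying disease, other drug(s)/vaccine(s), or other host or environmental factors". A second drug therefore counts against a Merck-product relationship.
- **Action taken:** "Did the adverse event cause Merck product to be discontinued".
- **Seriousness:** defined by events occurring during use of the Merck product. The exposure, time-course, dechallenge and rechallenge rows name the Merck product too.

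Section 7.2 limits the term Merck product to items "manufactured by, licensed by, provided by or distributed by Merck for human use". Section 9.1 names two suppliers: "Clinical Supplies will be provided by Merck and Vascene as summarized in Table 7".

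The safety objective (Section 3.3) is: "Determine the unique toxicities of the combination of pembrolizumab and sEphB4-HSA". In Section 8.2, the first TOX criterion counts "any toxicity (at least possibly related to treatment) that lead to treatment discontinuation prior to the start of the 3" (that is, the third) course.

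**The concern.** sEphB4-HSA is the less established of the two drugs, and the trial has to learn how the pair is tolerated. Section 5.4.2 already links hypertension to sEphB4-HSA. Under Table 6 as written, hypertension judged due to sEphB4-HSA alone would receive the same code as an event due to the tumour or an unrelated illness. If it led to stopping sEphB4-HSA, Table 6 would not record that link. Sections 5.2.1.2 and 5.2.1.3 allow either drug to continue alone, so a single action item cannot describe what happened.

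At stake are the treatment-related discontinuation rate (Section 4.2.3.1), any table of related events by agent, and the traceability of sEphB4-HSA dose decisions to the events behind them.

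**Working it through.** **Step 1: is sEphB4-HSA a Merck product?** Section 7.2 ties the term to Merck's manufacture, licence, provision or distribution. Section 9.1 names two suppliers, and Table 7 lists pembrolizumab and sEphB4-HSA. Section 7.2.3.1 names a Vasgene product alongside the Merck one. Read together, sEphB4-HSA is the Vasgene product and falls outside the definition.

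**Step 2: which code does the scale give?** For an event due to sEphB4-HSA alone, another drug explains it better than pembrolizumab does, so the answer is No. For an event due to both drugs, Yes remains possible, but the answer cannot show sEphB4-HSA's part.

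**Step 3: set Table 6 beside the sections that use the information.**

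| Section | What it needs or says | What Table 6 gives |
|---|---|---|
| 7.1.2.1 | Causality, and action on trial treatment | Merck product only |
| 7.2.3.1 | Seriousness and SAE relatedness for either company's product | Seriousness and relatedness for Merck product only |
| 4.2.3.1 | Rate of treatment-related toxicity leading to discontinuation | Relatedness and discontinuation for one drug |
| 5.2.1.3 | Toxicity related to sEphB4-HSA, leading to hold, reduction or stop | Neither item |
| 8.2, TOX | Relatedness to treatment as a whole | Relatedness to one drug |

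The first two rows are inconsistencies within the protocol. The last three are needs that Table 6 does not meet.

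**Step 4: what is kept.** Section 7.2 requires all adverse events to be reported from allocation to 30 days after treatment, and Section 8.2 tabulates them. Section 7.2.3.1 covers SAE relatedness for both products. Section 7.1.1.7 takes doses and dates of both drugs from pharmacy and nursing records, so a stop of sEphB4-HSA is documented, though not tied to an event. The gap is attribution by agent and the event-to-action link, mainly for non-serious events.

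**Step 5: the TOX boundary, as illustration only.** Section 8.2 uses a sequential probability ratio test with α = β = 0.10, p0 = 0.10 and pa = 0.30. The upper limit is

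N_X = floor{[X·ln(pa(1−p0)/(p0(1−pa))) − ln((1−β)/α)] / ln((1−p0)/(1−pa))}
= floor{[X·ln(0.27/0.07) − ln 9] / ln(0.9/0.7)}.

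For X = 3, 4, 5, 6 the bracketed values are 7.37, 12.74, 18.11 and 23.49, giving 7, 12, 18 and 23. This matches the printed table.

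The flag probability comes from an exact recursion. Let f_n(x) be the probability of x counted TOX among n patients with no crossing so far. Each new patient adds a counted TOX with probability p. The path stops as a flag if the new total X is 3 to 6 and n ≤ N_X. This is summed over 25 patients, taking TOX as classified in enrolment order. With every event counted, the result is 5.7% at p = 0.10 and 78.9% at p = 0.30.

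Now suppose, as an assumption, that TOX were counted from the Table 6 Yes code and the true rate is 30%:

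| Share of TOX not counted (assumed) | Counted rate | Flag probability |
|---|---|---|
| 0% | 0.30 | 79% |
| 25% | 0.30 × 0.75 = 0.225 | 51% |
| 50% | 0.30 × 0.50 = 0.15 | 19% |
| 75% | 0.30 × 0.25 = 0.075 | 2% |

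**The case against.** **The form has not been seen.** Table 6 calls its criteria guidance, and data are entered in eCRFs (Section 10.2.4.4) that are not in the documents. A second attribution item there would close the data gap. This stands as a limit. But the guidance label attaches to the criteria for reaching an answer, while the items to be evaluated are fixed, and Table 6 is the only item-level specification available. The protocol text would need aligning in any case.

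**No is the wrong code.** A reader might infer this, and the documents do not support it. No is the correct answer to a question about the Merck product when sEphB4-HSA alone caused the event. The fault is the missing parallel question.

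**The tolerability flag will come late.** A reader might infer this too. Section 8.2 defines TOX in its own terms, as possible relatedness to treatment, and does not refer to Table 6. The thresholds also differ: the Table 6 Yes describes an event more likely due to the Merck product than to another cause. The second TOX criterion, on slow-resolving immune-related toxicity, names no product. The documents neither make the link nor give an uncounted share.

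**The safety objective cannot be answered.** This also goes too far. Unique toxicity of the pair means toxicity beyond what the two drugs bring separately, and the tabulation of all events bears on that directly. Attribution by agent helps, but does not settle it.

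**Conclusion.** Table 6 is inconsistent with Sections 7.1.2.1 and 7.2.3.1 and does not supply the relatedness and action information that Sections 4.2.3.1, 5.2.1.3 and 8.2 rely on. If it is followed as written, events due to sEphB4-HSA alone cannot be told apart from unrelated events on the relationship item, and the link from an event to stopping sEphB4-HSA is not recorded. The loss falls mainly on non-serious events.

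The conclusion assumes that data collection follows Table 6 and that the eCRF has no second attribution item. The fall in flag probability from 79% to 51% or 19% needs two further assumptions, a count of TOX from the Table 6 code and a 25% or 50% uncounted share, so it is not an estimate of harm to the monitoring. The primary response endpoint is not affected. This should be corrected because the safety reading of the newer drug depends on it and the change is small.

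**What to change.** 1. In Table 6, and in the eCRF where lacking, record causality separately for pembrolizumab and for sEphB4-HSA. Do the same for action taken. Keep the two items apart and derive relatedness to either agent at analysis.
2. Align the Table 6 seriousness wording with Section 7.2.3.1, so that it covers both companies' products.
3. State in Section 8.2 that drug-related, and related to treatment, mean related to either agent. Say which data item feeds the Section 4.2.3.1 discontinuation rate and the TOX count.
4. If the eCRF lacked the sEphB4-HSA item, query attribution and action once for events already entered.
5. The rechallenge row names only the Merck product. The sponsor should reconcile it with the rest of the protocol; no rule is proposed here.

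The cost is protocol wording, a few eCRF fields if they are absent, and one retrospective query in a trial planned at 25 patients per cohort, with the NSCLC cohort already closed. Attribution made in retrospect is weaker than attribution made at the time and should be marked as such. Reported related-event rates may rise once sEphB4-HSA events are included.
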